In order to be consistent with the risk communication literature and maximize behavior change, this version of the CPS recommendations communicates the risk reduction and rationale (in a lay-friendly, succinct manner avoiding statistics) behind each stage's recommended restraint configuration, starting first with the basic rationale for occupant restraints, and moving into rationale for specific restraint configurations for the various child sizes. For example, many parents lack the understanding that an object in motion remains in motion when the vehicle crashes, unless restrained. They also fail to grasp that given the abrupt changes in momentum and velocity that occur in mere fractions of a second, crash forces are quite powerful and can result in a child propelling forward with the force of thousands of pounds. Similar to alternate one, this version of recommendations also includes pictures to illustrate stages of restraints, removes almost all references to age and upper limits for common seats, and fully integrates and highlights the need for back seat positioning at all stages. (Appendix E; Illustration 3)

*Comparison: Current CPS Recommendations.* Participants assigned to this condition will view NHTSA's current CPS recommendations as depicted in the "Car Seat Recommendations for Children" flyer released March 2011 (NHTSA, 2011). (Appendix E; Illustration 4)

*Control Group.* Participants assigned to this condition will not receive any instructional materials related to CPS during their participation. Rather, these participants will be taken through a computerized pictorial display of various child safety seats and motor vehicles currently on the market and asked to rate their preferences based on style, color, and other characteristics (See Appendix F). This subterfuge will allow for elapsed time between their pretest and posttest measures as in the other study conditions. To avoid a missed opportunity to educate, control group participants (and all participants) will be given a handout on child passenger safety to take home for reference once they have *completed* participation in the study (see post-study information handout in Appendix M).

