## **Measures**

Several measurement scales will be used to assess appropriateness of restraint selection, knowledge of restraints, perceived efficacy and threat, attitudes and intentions, judgments of relevance and acceptability of the CPS information, and sample demographics. To accurately assess changes in knowledge and perceptions after exposure to the independent variable, most measures will be asked both at pretest and posttest. The exceptions are the demographics questions and judgments of relevance and acceptability, which will be asked only at posttest (see survey attachment in Appendix H).

*Restraint Selection Task.* A key dependent variable for Study 1 is proper child restraint selection; thus, a Restraint Selection Task was developed that provides participants with a series of specific scenarios that ask the participants to select an appropriate restraint, direction to face, and/or vehicle row, given specific age/weight/height information for a hypothetical child. This 8-item knowledge measure uses a multiple choice response format (providing an item score of correct/incorrect and a total number correct score for each participant). This measure was adapted

from a similar existing field-tested measure (Snowden et al., 2008).

*Knowledge of Restraint.* To gauge immediate changes in knowledge of child passenger safety, as well as differences in knowledge among the groups, a 15-item assessment of parental knowledge will be conducted at both pretest and posttest. This measure uses a Likert-type response format and was tailored for this study from existing field-tested and validated measures used in past research by Snowden and colleagues (2008, 2009), and Will and colleagues (2009). Many questions originated from the Co-Investigators Kids in Kars Survey which has excellent internal consistency ( $\alpha = .92$ ) and measures parents' knowledge of and attitudes toward recommended guidelines for restraint use (Will, Sabo, & Porter, 2009).

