*Perceptions of Efficacy and Risk.* The Risk Behavior Diagnosis Scale (RBDS) (Witte, Cameron, McKeon, & Berkowitz, 1996) will be used to assess perceived efficacy and risk. The RBDS is a 12-item template survey designed to be tailored for assessment of any health or safety message. The efficacy subscale (internal consistency  $\alpha = .79$ , 6 items) assesses participants' perceptions of response efficacy (i.e., confidence that the recommended actions/restraints will work to prevent injuries) and self-efficacy (i.e., confidence in one's ability to follow child passenger safety recommendations). The threat subscale (internal consistency  $\alpha = .82$ , 6 items) assesses participants' perceived risk by measuring susceptibility to and severity of negative consequences from inappropriate child occupant protection. Four additional "severity" items were added to properly assess perceptions of severity of the threat at each of the four stages of occupant protection. This, the final RBDS contains 16 items, all of which use a 5-point Likert-type response scale (1 = strongly disagree to 5 = strongly agree).

*Attitudes and Intentions.* Participant's more general attitudes and intentions regarding child passenger safety will be assessed via an 8-item attitudes subscale, adapted from the previously mentioned Kids in Kars survey (Will, Sabo, & Porter, 2009), and a 9-item stated intentions subscale. Stated intentions and attitudes will be assessed to gauge participants' disposition regarding what is recommended for child occupant protection irrespective of their knowledge. Both subscales use a Likert-type response format (1 = strongly disagree to 5 = strongly agree).

*Judgments of Relevance and Acceptability.* At posttest, parents in each condition will be asked their opinions about the CPS materials. A 10-item questionnaire was developed that uses a 4-point Likert-type response format to assess participants' judgments of quality and acceptability of the CPS information presented. Specifically, they will be asked to rate the CPS information on a variety of factors, including but not limited to style, amount of information, clarity, and likelihood for motivating behavior change.

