### ***Data Analysis Plan***

Data analysis will determine which CPS recommendation version produces the maximum desired outcome (e.g., correct CPS restraint selection, increased knowledge of restraints, enhanced perceptions of efficacy and risk). Data analysis will begin with data cleaning such as checking for missing data and outliers and ensuring normality and linearity of all dependent variables. Next, bivariate correlations will be conducted on all dependent variables to assess their relation to each other and to determine the type of inferential statistics to conduct. Specifically, if dependent variables are moderately inter-correlated, then a 2 (Time) x 5 (CPS Recommendation Version) MANOVA with follow-ups, post-hoc test for group, and simple effects analyses (if the interaction is significant) will be conducted. If dependent variables exhibit inter-correlations near zero or are highly inter-correlated, then multiple 2 (Time) x 5 (CPS Recommendation Version) ANOVAs with post-hoc test for group and simple effects analyses (if the interaction is significant) will be conducted. In the event that the data are found to violate the assumptions of normality that are necessary for parametric tests, data transformations to improve normality or appropriate nonparametric tests, such as the Friedman test and follow-up Multiple Comparison Tests, will be performed instead. Additionally, the study team may conduct several secondary analyses, including a multiple regression for CPS restraint selection to determine which CPS recommendation version best predicts correct restraint selection. Also, variables such as perceived relevance and accuracy of CPS information, age, sex, race, education, income, number of children, and ages of children may be used as covariates to eliminate potential confounding variables and better explain variance in the analyses. The results of Study 1 will be written into a brief research report for NHTSA. No reports or presentations will identify individual participants.

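### Both studies allow post-exposure ratings of the CPS information as covariates against confounding, although the assigned message can itself change those ratings

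*Protocol*

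**What the plan says.** In the Study 1 Data Analysis Plan, the list of possible adjustment variables opens with "variables such as perceived relevance and accuracy of CPS information, age, sex, race, education, income" and goes on to number and ages of children. These "may be used as covariates to eliminate potential confounding variables and better explain variance in the analyses". The Study 2 Data Analysis Plan has the same list and the same purpose.

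The Study 1 Measures section fixes when the ratings are taken: "The exceptions are the demographics questions and judgments of relevance and acceptability, which will be asked only at posttest". Study 2 repeats this. The questionnaire assesses "participants' judgments of quality and acceptability of the CPS information presented", and its topics include how likely the information is to motivate a change in behavior.

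On who answers, the same section says: "At posttest, parents in each condition will be asked their opinions about the CPS materials". The Control Group paragraph of the Study 1 Study Conditions says that participants in that arm "will not receive any instructional materials related to CPS during their participation". They view pictures of child seats and vehicles and rate them on style and color.

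**The concern.** Allocation is randomized in both studies, so a reaction to the assigned message cannot confound the effect of that message. It comes after the message and may be one of the routes by which the message works. Holding it fixed changes the question from how well a version works to how well it works apart from being judged relevant or accurate. If an unmeasured trait, such as general interest in safety, drives both the rating and the outcome, adjustment also links that trait to the arm and can produce a difference where none exists.

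The protocol's purpose is to tell NHTSA which version or combination performs best. An adjusted comparison could understate a version that works partly by seeming more relevant, or shift the comparison between versions for reasons unrelated to their effect. In Study 1 there is a further difficulty: in the Control arm it is unclear what the rating would refer to.

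**Working it through.** **Timing and content.** The protocol gives no figure to reproduce, so the check starts from the text.

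1. The relevance and acceptability ratings have no pretest value and follow exposure (Measures).
2. They judge the information presented, which is what differs between arms (Measures; Study Conditions).
3. Parent preference among versions is a stated aim of Study 1 (Study Design), so the plan itself expects that versions may differ on such ratings.
4. Accuracy is not among the aspects that the questionnaire description names, but that list is not exhaustive. Its posttest timing is inferred.
5. Demographics are also asked only at posttest, but the message cannot change age, sex, race, education, income, or number and ages of children. The objection does not reach them.

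**Size, under assumed values.** Let *a* be the shift in the rating caused by a version (in SD) and *s* the within-arm slope of the outcome on the rating (SD per SD). In a linear model:

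adjusted effect = total effect − *a* × *s*

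Neither *a* nor *s* is in the protocol. Taking *a* from 0.3 to 0.8 and *s* from 0.2 to 0.4:

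- low: 0.3 × 0.2 = 0.06 SD
- middle: 0.5 × 0.3 = 0.15 SD
- high: 0.8 × 0.4 = 0.32 SD

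If *s* reflects a causal path from rating to outcome, this amount is true effect removed. If *s* reflects a shared cause, it is a spurious shift.

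**Simulation.** Two arms of 60 (300 / 5, assuming equal allocation), 4,000 runs, linear regression with and without the rating as a covariate. The version raises the rating by 0.5 SD except in the last row.

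| Assumed situation | Effect, unadjusted → adjusted | Rejection rate at 5%, unadjusted → adjusted |
|---|---|---|
| Half of a 0.50 SD effect runs through the rating | 0.50 → 0.25 | 78% → 32% |
| One quarter of it does | 0.50 → 0.37 | 78% → 52% |
| Half of it does, plus a shared unmeasured cause | 0.50 → 0.17 | 78% → 22% |
| No true effect, shared unmeasured cause | 0.00 → about −0.13 | 5% → 10% |
| Version does not change the rating | 0.50 → 0.50 | 76% → 87% |

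The formula agrees with the first row: 0.50 − 0.5 × 0.5 = 0.25. In the fourth row the simulated slope is 0.5 × 0.5 = 0.25, so the shift is 0 − 0.5 × 0.25 = −0.125. The last row shows the attraction of the covariate, a gain in precision, and the condition for it: the versions must leave the rating unchanged.

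**Control arm, Study 1.** Every condition rates the CPS materials, but Control receives no CPS instructional material. A Control rating, if given, has a different referent from the other four arms. If it is left blank, a complete-case adjusted model loses the arm, about 60 of 300 participants under equal allocation. Study 2 has no such arm: all four conditions view the recommendations.

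**The case against.** The strongest reply is that nothing commits the study to this adjustment. The main tests are a MANOVA or ANOVAs named without covariates. The covariate sentence follows one on optional secondary analyses and is itself permissive. That stands, and it limits the point to what could happen if the option is used. It does not remove the point: the sentence refers to the analyses generally, confines the ratings to no mediation analysis, and gives a reason, confounding, that is wrong for them.

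A reader might go further in four ways that the protocol does not support:

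- *That a version working through relevance would look no better than the others after adjustment.* This needs the whole effect to run through the rating; otherwise only part is lost.
- *That the loss matches or exceeds the effect of 0.25 named in the Sampling Plan.* Of the three assumed cases, 0.06 and 0.15 lie below 0.25 and only 0.32 lies above it. All rest on assumed inputs.
- *That the Time by Version model, or a five-group preference test including Control, is planned for the ratings.* The Data Analysis Plan does not say so. Its named example outcomes are restraint selection, knowledge, efficacy and risk, and the analysis of a posttest-only scale may be left to a separate plan.
- *That the Control parents' style and color ratings are their relevance ratings.* The picture task and the posttest questionnaire are separate instruments. The appendices with their wording are not in the document at hand. What can be said is that the text leaves unclear what Control would be judging.

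**Conclusion.** The point holds in a limited form. Both Data Analysis Plans permit adjustment for a response to the randomized message and call it control of confounding. If used, the adjustment could remove mediated effect or introduce collider bias. It does no harm only if the versions do not alter the rating, which cannot be presumed in a study that sets out to compare parents' preferences among versions.

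The size cannot be derived from the protocol. The range of about 0.06 to 0.32 SD and the simulated losses of power are illustrations that depend on the assumed shift and slope. The argument on timing is firm for relevance and acceptability and inferred for accuracy. The lack of comparability in the Control arm is an added reason in Study 1 only.

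**What to change.** In the Data Analysis Plans of both studies, delete perceived relevance and accuracy of the CPS information from the covariate list, and state that covariates are limited to characteristics that the message cannot change, namely the demographics already listed.

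Add one sentence: the ratings are used only as posttest outcomes or in a mediation analysis labelled exploratory, and in Study 1 these uses are restricted to the four message arms. Study 2 needs no such restriction, because every arm views CPS recommendations.

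The cost is one deletion in each of two places and a short addition. No data collection, sample size or main test changes. Any precision that the ratings might have added is given up.

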### ***Study Conditions***

Participants will be electronically randomized into one of five groups to examine relative effectiveness of and parent preferences for different methods of framing child passenger safety (CPS) recommendations. The five study conditions (four versions of CPS recommendations and one control group) are described below and are included in the attachments.

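### Both analysis plans allow posttest ratings of the assigned message as covariates against confounding; such ratings cannot confound a randomised comparison, and adjusting for them can distort the message effect

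*Protocol*

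**What the plan says.** The Data Analysis Plan for Study 1 ends its methods with a list of possible covariates. It opens with "variables such as perceived relevance and accuracy of CPS information" and continues with age, sex, race, education, income, and the number and ages of children. The plan says that these "may be used as covariates to eliminate potential confounding variables and better explain variance in the analyses". The Study 2 plan repeats the list and the purpose.

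The Measures section for Study 1 fixes when the materials are judged: "The exceptions are the demographics questions and judgments of relevance and acceptability, which will be asked only at posttest". It adds: "At posttest, parents in each condition will be asked their opinions about the CPS materials". The rated aspects include "style, amount of information, clarity, and likelihood for motivating behavior change". Study 2 uses the same questionnaire, again once, at posttest.

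Assignment is by electronic randomisation, and preference is part of the aim: "Participants will be electronically randomized into one of five groups to examine relative effectiveness of and parent preferences for different methods of framing". The Study 1 control parents "will not receive any instructional materials related to CPS during their participation"; they rate pictures of child seats and vehicles instead.

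**The concern.** A confounder of a message comparison must be related to assignment for some reason other than the message itself. Under randomisation, a parent's opinion of the assigned version is not such a variable. It arises after exposure and may be caused by the version. Putting it in one list with age and education, for a shared purpose, treats a possible effect of the message as a baseline characteristic.

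Two kinds of harm can follow. If a version works partly because parents find it more relevant or motivating, holding the rating fixed subtracts that part of the benefit. If an unmeasured trait, such as motivation, drives both the rating and the posttest score, conditioning on the rating unbalances that trait between arms, and a difference can appear where the message does nothing. Both require the versions to differ in rating. The preference aim shows that the investigators regard this as an open question.

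At stake is the total effect of each version, which is what the study needs in order to say which version performs best.

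**Working it through.** **Timing and content.** The plan states no figure on this point, so the first check sets the sections side by side.

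- Assignment is randomised and precedes exposure (Study Conditions).
- Exposure precedes the judgments, which have no pretest value (Measures, both studies).
- The judgments concern the presented materials and include their power to motivate, a plausible route to the outcomes.
- The rating is therefore a possible mediator, or a variable affected by both message and parent traits. It is not a confounder.
- Demographics are also recorded at posttest, but a message read in the session cannot plausibly change them. The objection does not extend to them.

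**Illustration of size.** From the protocol: 300 / 5 = 60 and 240 / 4 = 60 parents per arm, if allocation is equal (an assumption). Assumed, because the documents do not give them: pretest-posttest correlation 0.5, within-arm SD 1 for rating and posttest, rating shift s = 0.5 SD between two arms, and within-arm slope b of posttest on rating given pretest. The two-sided 5% critical value is taken as 1.98.

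*Without the rating.* Residual variance = 1 − 0.5² = 0.75. SE = √(0.75 × 2/60) = 0.158. For a true effect of 0.50, power = Φ(0.50/0.158 − 1.98) = Φ(1.18) = 88%.

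*With the rating, mediator case (b = 0.4, rating unrelated to pretest).*

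- Estimate = total effect − s × b = 0.50 − 0.5 × 0.4 = 0.30.
- Residual variance = 0.75 − 0.4² = 0.59.
- SE = √(0.59 × (2/60 + 0.5²/118)) = √(0.59 × 0.03545) = 0.145.
- Power = Φ(0.30/0.145 − 1.98) ≈ 54%.

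A simulation of 4,000 trials under these inputs gave 88.4% and 54.1%.

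*Zero true effect, shared cause.* The adjusted estimate is −s × b. If the rating correlates r with posttest and q with pretest, b = (r − 0.5q)/(1 − q²). The residual variance is 0.75 − b²(1 − q²), and SE = √(residual variance × (2/60 + s²/(118(1 − q²)))). Type I error = Φ(|est|/SE − 1.98) + Φ(−|est|/SE − 1.98).

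| r with posttest | q with pretest | b | Adjusted estimate | SE | Type I error |
|---|---|---|---|---|---|
| 0.3 | 0 | 0.30 | −0.15 | 0.153 | about 16% |
| 0.4 | 0 | 0.40 | −0.20 | 0.145 | about 27% |
| 0.3 | 0.3 | 0.165 | −0.08 | 0.161 | about 8% |
| 0.4 | 0.4 | 0.238 | −0.12 | 0.159 | about 11% |

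The simulation for the first two rows gave 16.7% and 27.5%.

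*No rating shift.* With s = 0 the term s × b vanishes. The estimate is unbiased and type I error stays at 5%, whatever the shared cause.

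**The case against.** The strongest reply is that nothing commits the study to this adjustment. The wording is permissive, the list is illustrative, and the MANOVA or ANOVA that forms the specified analysis names no covariate. The sentence follows directly on the optional secondary analyses. This stands, and it lowers the severity. It does not remove the point, because the sentence refers to the analyses without limit and gives no rule for when the option is taken. The stated purpose also includes explaining variance, which is legitimate for baseline characteristics.

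Four stronger readings are tempting, and the documents do not support them:

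- **Adjustment always biases the comparison.** It does so only if the versions differ in rating. The three alternates in Study 1 share several features, and every Study 2 arm contains the Condition 1 material, so some differences may be small.
- **The control arm would be lost from the adjusted model.** Parents in every condition are to be asked, so a control rating may exist. What stands is that it would not be comparable, since these parents see no CPS instructional material. Study 2 has no such arm.
- **Perceived accuracy is never measured.** The questionnaire's description is explicitly not exhaustive and its items are in Appendix H, which is not shown. Equating the covariate with the relevance and acceptability scale is an inference. The argument does not depend on it, because any rating of the presented information comes after exposure.
- **The ranking of versions will be reversed.** This would need particular differences in rating between versions, and the protocol gives none.

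**Conclusion.** The point holds as a defect in an optional clause. Both plans permit a post-exposure rating of the randomised message as a covariate and give removal of confounding as part of the reason, a task that the rating cannot perform. If it is used in a model for the message effect, and if ratings differ between versions, the estimate no longer measures the total effect of the version.

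The size cannot be computed from the protocol. In the illustration the estimate falls by 0.20 SD (0.50 to 0.30), or type I error reaches roughly 8% to 27% in place of 5%. The lower end applies when the rating correlates with pretest as strongly as with posttest, the upper end when it is unrelated to pretest. All of this rests on the assumed shift, slope and correlations.

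It should be fixed before analysis. It does not show that the specified main analysis is biased.

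**What to change.** In the Data Analysis Plans of both studies, delete the item on perceived relevance and accuracy from the covariate list, and state that it is also kept out of the secondary multiple regression. Limit covariates to pretest scores and to characteristics that the message cannot change (age, sex, race, education, income, number and ages of children), and give precision as their purpose.

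Analyse the ratings as an outcome among the arms that received a message, which serves the preference aim directly. If the route of the effect is of interest, use a separately labelled mediation analysis that does not decide which version is best.

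The cost is one sentence in each plan and no new data. The variance that the rating would have explained is given up.
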